## 1. LIST OF ABBREVIATIONS

GCP: *Good Clinical Practice*DSMB: *Data Subject Monitoring Board*ASI: *Air Susu Ibu*RCT: *Randomized Control Trial*CTP: *Computed Tomography Perfusion*

## 2. STUDY SYNOPSIS AND SCHEMA

## Study Synopsis

[figure not shown]
Title	Efficacy of ASIMOMMY® Compared to Domperidone and Placebo in Increasing Breastfeeding: Randomized Single-Blind Controlled Trial in Indonesia.
Purpose	Assessing the efficacy of ASIMOMMY® in increasing breast milk production in postpartum mothers.
Hypothesis	ASI MOMMY® increases milk production in postpartum mothers.
Methodology	
Study Design	Randomized Control Trial (RCT) .
Study Time	October 2022 until March 2022.
Study Location	Tegalrejo and Jetis Primary Health Care, Yogyakarta.
Study Product	
Treatment group	ASI MOMMY®.
Control group:	Domperidone and placebo.
Subject Criteria:	
Inclusion Criteria:	
 
Mothers 20-35 years old.
 
Gestational age at delivery 37-40 weeks.
 
Vaginal delivery.
 
Normal body mass index (BMI 18.5-24.9 kg/m^2).
 
Not taking drugs or breast milk enhancement supplements.
 
Healthy mother's condition with normal nipples (protruding).
 
Healthy baby condition with good suction reflex.
 
The baby consumes only breast milk.
 

Exclusion criteria:	
 
Allergy to ASI MOMMY® and Domperidone.
 
The mother is taking medications that affect the effects of domperidone (such as antacids, cimetidine, ranitidine, famotidine and nizatidine) or medications that interact with domperidone (such as haloperidol, lithium).
 
The mother is in a state of illness requiring hospitalization.
 
Mother has HIV AIDS, heart problems, mastitis, and had undergone breast surgery.
 
Underweight, overweight and obese mothers.
 
Giving birth to twins.
 
The baby has a congenital defect that affects the suctioning process of breast milk
 

	
 
• Infants and mothers who did not participate in the treatment until completion (day 7 of the intervention).
 

Sampel size	The sample size was 15 subjects per group. The total sample size was 45 subjects.
Subject Allocation Method	Randomization with a randomization list.
Intervention	
 
• Beginning of the study is on day 3 postpartum, the initial baby weight was weighed before the start of the intervention.
 
• The weighing was conducted at Tegalrejo and Jetis Primary Health Center, at 08.00-10.00 WIB using Onemed OD-231 digital baby scales with an accuracy of 0.01 kg. When weighing the baby did not wear clothes or pampers.
 
• Body weight weighing was carried out at Tegalrejo and Jetis Primary Health Center, at 08.00-10.00 WIB using Onemed OD-231 digital baby scales with an accuracy of 0.01 kg. When weighing babies do not wear clothes or pampers.
 
• Intervention starts on the 3rd day postpartum until the next 7 days (10th day postpartum) with drug administration.
 
• The intervention provided will be single-blind, the packaging will be similar, and neither the research assistant nor the subject will know the type of intervention provided. Administration of domperidone in capsule preparation at a dose of 10 mg orally taken every 8 hours, 3 times a day, for 7 days, at 06.00, 14.00, and 22.00 WIB. ASIMOMMY® and placebo in capsule preparation were taken once a day, at night, as much as 2 capsules, for 7 days. Each subject will get all capsules on the first day to be taken for 7 days.
 
• Evaluation of the baby's weight was done by re-weighing the baby's weight on the 7th day of the intervention. Then the baby's weight gain was assessed, which was obtained from the difference between the baby's weight on day 7 of the intervention and the baby's weight on day 0 (before the intervention).
 

Duration of intervention	7 days.
Study Outcomes	Breast milk production was measured by assessing the infant's weight gain, which was obtained from the difference between the infant's weight on day 7 of the intervention and the infant's weight on day 0 (before the intervention).
Statistical Analysis	Statistical data analysis in this study used the SPSS version 24.0 program. Data were tested for normality first to determine the statistical analysis test used next. Research results with categorical data (nominal and ordinal) are displayed in the form of number/frequency and percentage of each group. Numerical data that is normally distributed (parametric) will be displayed in the mean and standard deviation, while if the data is not normally distributed (non-parametric) it is displayed with the median, minimum and maximum values.

Chi Square test was used for variables with categorical data (nominal and ordinal). The bivariate analysis test used for variables with numerical data (parametric) is One Way Anova with Post Hoc Bonferroni, while for non-parametric is Kruskall Walis with Post Hoc Mann Whitney.

The analysis test for external variables with parametric data and dependent variables was carried out with the Pearson correlation test, while for non-parametric data it was carried out with the Spearman correlation test.

Synopsis or Schema:

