## 9. STUDY POPULATION

### a. Subject Recruitment

Data collection is done by healthcare providers on duty. Data collection is conducted starting from July 2022 until December 2022 by finding information about mothers in labor from Jfestis and Tegalrejo public health centers. Women in

puerperium who meet the inclusion and exclusion criteria are gathered in the research until the number of samples needed is fulfilled.

The researcher explains the research intent, method, and procedure that will be done to the mother. Then the mother is allowed to sign the informed consent form if they agree to become a research subject. The research subjects are given lactation counseling. Next, the research subjects are randomized by the researcher using the random number table with each group containing 15 subjects. The researcher will allocate each group with one type of treatment, that is drug A, drug B, and drug C, then randomization is conducted. The list of randomizations is kept by the researcher.

b. Populasi

The subject population in this research are postpartum women from Tegalrejo Public Health Center and Jetis Public Health Center in Yogyakarta who plan to breastfeed their baby.

c. Inclusion Criteria

- a. Gestational age 37-40 weeks at labor
- b. Giving birth vaginally
- c. Normal body mass index (BMI 18.5-24.9 kg/m^2)
- d. Does not consume drugs or supplements to enhance breastmilk
- e. Healthy women with normal nipple condition (protrudes)
- f. Condition of baby is health with good suction reflex
- g. Baby currently only consumes breastmilk

d. Exclusion Criteria

- a. Allergy towards ASI MOMMY® and Domperidone
- b. Women who consumes drugs that influences the effects of domperidone (such as antacids, cimetidine, ranitidine, famotidine, and nizatidine) or drugs that interacts with domperidone (such as haloperidol, lithium).
- c. Women who are in sick condition and needs in-hospital treatment
- d. Women with HIV AIDS, heart problems, mastitis, and a history of breast surgery
- e. Underweight, overweight, and obese women
- f. Twin pregnancies
- g. Babies born with a congenital disease that affects the breastfeeding process
- h. Babies and mothers who do not follow the regimen from start to finish (seventh day of intervention)

e. Number of CTP Sites

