## 10. CLINICAL TRIAL PROCEDURE

a. Recruitment and Enrollment

The research team will fill the recruiter information log sheet. All subject candidates will receive starting information and disclose their willingness to participate in the clinical trial and consent to give information about their phone number and home address.

b. Recruitment Plan

Research subject candidates are recruited until the amount of subjects fulfill the minimal sample amount that has been determined by the research team.

c. Initial Subject Screening

During initial screening the screening form will be filled, the researcher will fill the screening log, and if the subject candidate fulfills the inclusion and exclusion criteria of the research, they will be given a subject ID number by the research team.

d. Informed Consent Procedure

Research subjects will be given starting information and be given the opportunity to ask questions if they still have questions regarding the research. After it is made sure that the research subjects have understood and received information about the research, the doctor or midwife on site will ask for the subject's signature for willingness to participate in every step of the research.

e. Baseline Assessment

This study includes interviews related to the demographic data of the subjects.

f. Randomization

Randomization using random numbers that is obtained from the random numbers table. The randomized list is placed inside a non-transparent, sealed envelope and is given serial numbers according to the number of subjects. The envelopes are held by one of the researchers and kept in the Center. Every subject that fulfills the criteria to participate in the research will be reported to the Center and Research Site, and an envelope is taken according to the serial numbers.

g. Treatment

i. Subject Discontinuation Criteria

In this research, the criteria for sample drop out includes subjects/babies who are sick and cannot continue participating in the research, babies who drink baby formula during the intervention, and subjects who consecutively skips consuming the capsules.

Termination of the intervention is done if the subject experiences side effects or serious adverse effects and will be examined by the research doctor for further observation and will receive treatment according to the research flow and placed in the intervention termination form.

ii. Treatment Discontinuation

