Statistical data analysis in this study is done using SPSS 24.0 program. The data undergoes normality testing first to determine which statistical analysis test will be used. The result of research with categoric data will be presented in the form of quantity/frequency and percentage from each group. Numeric data with normal distribution (parametric) will be presented in the form of average and standard deviation, whereas if the data is not distributed normally (non-parametric) then it will be presented using median, minimal value and maximum value.

d. Significance Testing

Chi-squared test is used for variables with categoric data (nominal and ordinal). Bivariate analysis test that is used for variables with numeric data (parametric) is the One Way Anova test with Post Hoc Bonferroni, meanwhile for non parametric data is Kruskall Walis with Post Hoc Mann Whitney.

Analytical test for variables aside from parametric data and dependent variables is using Pearson correlation, while non-parametric data is analysed using Spearman correlation

e. *Demographic and baseline Characteristics*

Research data with categoric data (nominal and ordinal) is presented in the form of quantity/frequency and percentage from each group.

f. *Safety Analysis*

The entire data analysis process will be done by a biostatistics expert appointed by the research team.

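### The arm comparison is fixed as an unadjusted test on raw weight gain with 15 babies per arm; it is valid, but it gives up precision that the measured day-0 weight could supply

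*Protocol*

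**What the plan says.** The Study Synopsis of the Protocol fixes the baseline: "Beginning of the study is on day 3 postpartum, the initial baby weight was weighed before the start of the intervention". Its outcome row measures milk production by infant weight gain, the "difference between the infant's weight on day 7 of the intervention and the infant's weight on day 0 (before the intervention". It also gives the size: "The sample size was 15 subjects per group. The total sample size was 45 subjects".

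Section 14.d fixes the comparison for numeric data as "the One Way Anova test with Post Hoc Bonferroni, meanwhile for non parametric data is Kruskall Walis with Post Hoc Mann Whitney". Neither test carries a covariate. The synopsis adds a correlation step, "The analysis test for external variables with parametric data and dependent variables was carried out with the Pearson correlation test", with Spearman as the non-parametric counterpart. The external variables are not named.

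On baseline data, Section 10.e says only "This study includes interviews related to the demographic data of the subjects". Section 13 lists physical examination, blood pressure and the baby's weight before and after treatment. The flow chart in Section 3 adds medical history and a physical examination that includes an undefined item, BW. Birth weight is not named anywhere. Sections 9.a and 10.f describe randomisation from a random number table and mention no stratification.

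**The concern.** A baby's gain from postpartum day 3 to day 10 may depend on its size and on how far its day-3 weight has moved from birth weight, whatever the mother takes. That dependence is an assumption; the Protocol gives no data on it. If it holds, part of the spread in gain can be predicted from what is known before treatment, and an unadjusted test leaves that part in the error term.

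Two things are at stake. The first is precision, in a trial with only 15 babies per arm. The second is interpretation: if the arms start apart by chance, a reader of the unadjusted result cannot tell how much of a difference in gain reflects the starting point. Day-0 weight is already measured, but the planned arm comparison uses it only for the subtraction. Birth weight may not be recorded at all, and no later analysis plan can adjust for a variable that was not collected.

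**Working it through.** **Inputs.** From the Protocol: three arms, 15 babies each, 45 in total; raw gain as outcome; no covariate; alpha 0.05. Not in the Protocol: the SD of the gain and its correlation r with the starting point. Everything below is therefore in SD units, over a range of assumed r.

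**The plan's own figure.** The 15 per group cannot be reproduced, because Section 14.b names a combined SD without a value. Its planning means (3426.6, 3221.1 and 3000) are body weights, not gains, so it says nothing about the SD of the gain or about r.

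**1. Subtraction does not remove the relation.** cov(gain, day-0 weight) = cov(day-7 weight, day-0 weight) − var(day-0 weight). This is zero only if the slope of day-7 on day-0 weight is exactly 1.

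**2. Chance imbalance at 15 per arm.**
- Standard error of a difference between two arms on a baseline factor: sqrt(2/15) = 0.365 SD.
- Expected absolute gap for one pair: about 0.8 × 0.365 = 0.29 SD. The 1.96-SE limit is 1.96 × 0.365 = 0.72 SD, which one pair exceeds only about 5% of the time.
- One given pair more than 0.5 SD apart: z = 0.5/0.365 = 1.37, two-sided probability 17%.
- At least one of the three pairs more than 0.5 SD apart: the range of three means must exceed 0.5 × sqrt(15) = 1.94 standard errors of a mean, probability about 36%. Simulation gives the same figure.

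**3. Type I error.** Simulated trials of 3 × 15 babies, 200,000 per setting, no treatment effect, one covariate:

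| Assumed r | ANOVA, all trials | ANOVA, some pair > 0.5 SD apart | ANOVA, other trials | ANCOVA, some pair > 0.5 SD apart |
|---|---|---|---|---|
| 0.3 | 5.0% | 6.3% | 4.3% | 5.1% |
| 0.5 | 5.1% | 8.5% | 3.2% | 5.1% |
| 0.7 | 5.0% | 11.2% | 1.5% | 4.8% |

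Unadjusted ANOVA keeps its level over all trials. ANCOVA stays near 5% in the imbalanced ones too.

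**4. Power.** For a 1-SD advantage in one arm (100,000 runs per setting, one covariate), unadjusted power is about 78%. ANCOVA gives 77%, 81%, 88% and 97% at r = 0, 0.3, 0.5 and 0.7.

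**5. Equivalent sample size, net of the cost of estimating covariates.** With q covariates, error variance is multiplied by (1 − r²), and the variance of an arm contrast rises on average by the factor 1 + q/(45 − 3 − q − 1). Equivalent n per arm = 15 / [(1 − r²) × factor], where r is the multiple correlation when q = 2.

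| Covariates | Factor | r = 0.2 | r = 0.4 | r = 0.5 |
|---|---|---|---|---|
| 1 | 1 + 1/40 = 1.025 | 15.2 | 17.4 | 19.5 |
| 2 | 1 + 2/39 = 1.051 | 14.9 | 17.0 | 19.0 |

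With two covariates, break-even is at r² = 1 − 1/1.051 = 0.049, or r of about 0.22.

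**The case against.** The strongest reply is that randomisation already deals with the starting point. Unadjusted ANOVA on gain is unbiased, its error term already contains the between-baby variation, and the natural weight course of the week is shared with the placebo arm. This stands. A reader might infer that chance differences at the start will pass for a milk effect more often than the nominal 5%. The documents do not support that. The 6% to 11% rates arise only after selecting the 36% of trials that turn out imbalanced, and lower rates in the other trials offset them. Nor is a gap of 0.7 SD typical; it is roughly the 1.96-SE limit.

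The spread at the start is also narrowed by design. Babies start on a common postpartum day and are weighed unclothed in a fixed morning slot on one scale model. Eligibility includes "Gestational age 37-40 weeks at labor", vaginal delivery, a healthy baby and breast milk only. This limits the likely r but does not set it to zero.

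A reader might also conclude that the starting point is not captured at all. That goes too far: day-0 weight is recorded, and BW in the flow chart or the medical history might include birth weight, though the text does not say so. Correlating unnamed external variables with the outcome is a look at prognostic factors, not an adjusted comparison of arms.

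Lastly, detail of this kind is often left to a statistical analysis plan, which was not available here, and the trial calls itself a pilot. But the Protocol is not silent: it names the outcome and the tests, and so fixes an unadjusted comparison.

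**Conclusion.** The point holds as lost precision and as a result that is harder to read under chance imbalance. It is not a bias or an inflated overall error rate. About 36% of trials of this size will have some pair of arms more than 0.5 SD apart on a given baseline factor, and the plan provides no adjusted comparison for that case.

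The size of the gain is uncertain. It rests on r, which the Protocol does not give. With two covariates, 15 per arm acts like 17.0 at r = 0.4 and 19.0 at r = 0.5, but like 14.9 at r = 0.2, a very small loss.

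The 5% figure assumes that the arms analysed are the arms randomised. Sections 9.d, 10.g.i and 10.g.iii exclude or drop some mothers and babies after allocation and allow replacement. The figures above do not cover any effect of that, and covariate adjustment should not be relied on to repair it.

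**What to change.** - In Section 14.d and the synopsis, make the primary analysis one ANCOVA of the three arms with day-0 weight as covariate and Bonferroni-adjusted pairwise contrasts. Gain or day-7 weight may be the response: with day-0 weight in the model the arm contrasts are identical, because the two responses differ only by that covariate.
- Keep the unadjusted comparison as a supporting result.
- In Section 10.e, copy birth weight from the delivery record where available, and define BW in the flow chart.
- Add birth weight minus day-0 weight as a second covariate. A baby without a birth weight would drop out of that model, so state in advance which model is then primary; the one with day-0 weight alone keeps every baby weighed at both visits.
- In Section 14.e, show day-0 weight and birth weight by arm.

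Cost: one or two of 42 error degrees of freedom, one case report form field and a sentence or two of analysis text. No extra visit or procedure is needed. If r proves weak, the price is the very small loss shown above.

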### 3. STUDY FLOW CHART OR TIME AND EVENT TABLE

Visit	Screening/ Baseline	Treatment/ Day 0	Day 7	Unscheduled Visit
Visit Window	-14 days	-	+0 –14 days	-
Informed Consent	✓			

Assign subject ID	✓			
Medical History	✓			
Inclusion/ Exclusion Criteria	✓			
Physical Exam (incl. temp, BP, BW)	✓			
Randomization	✓			
Treatment		✓	✓	
Adverse event				

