## 11. STUDY TREATMENT

a. Study Intervention

i. Active Group

The intervention group is the group of patients who receive ASI MOMMY® preparation.

1. Dose, Formulation, Rute, Duration, Hours, etc

ASIMOMMY® formula contains extracts of Katuk leaf (Sauvopis androgynous) 300 mg, Fenugreek (Trigonella foenum-graceum) 50 mg, and Moringae oleifera extract (Moringa leaf) 50 mg. The formulation is taken once a day at nighttime, as much as 2 capsules for a duration of 7 days ([name] et al., 2020). The capsule is taken once a day at nighttime at 20.00 as much as two capsules.

ii. Control group

The positive control group consists of patients who receive domperidone

1. Dose, Formulation, Route, Duration, Hours, etc

Domperidone that is used is 10 mg dosage, taken every 8 hours for 7 days (Paul et al., 2015). The drug is taken three times a day at 06.00, 14.00, and 22.00 West Indonesia Time.

iii. Placebo group

The negative control group consists of patients who receive placebo.

1. Dose, Formulation, Route, Duration, Hours, etc

Sugar inside the capsule does not give any therapeutic effect, is taken once a day, as much as 2 capsules, for duration of 7 days.

b. Dispense of Study Medications

At the first visit, research subjects are given all the drugs equivalent to the number of capsules that will be consumed for a week.

c. Drug Packaging/handling/Storage/Accountability

ASI MOMMY® is a polyherbal formula that is made in a capsule form by the herbal drug industry (PT Swayasa Prakarsa, Yogyakarta, Indonesia). This drug preparation is kept under 30 degrees celsius in a dry place away from sunlight.

Each capsule contains extracts of Katuk leaf 300 mg, Fenugreek 150 mg, and Moringa leaf 50 mg. ASI MOMMY® has undergone activity testing and acute and subchronic toxicity testing. Research has shown that ASI MOMMY® formula works actively as an herbal galactogogue drug and does not have give any toxic effects, therefore it is safe to be given to humans (unpublished data).

d. Training procedure

Training will be given by experts provided by the research team to the research members in two sites which includes materials about the SOP, protocols, and entire research flow.

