### 14. STATISTICAL ANALYSIS

a. General Design

The method used in this research is a single blind, Randomized Control Trial (RCT). The benchmark of this study is the measurement of the babies' weight before and after the intervention therapy that is given (the research product).

i. Hypothesis

**H0:** The traditional drug preparation ASIMOMMY® does not increase breastmilk production in postpartum women.

**H1:** The traditional drug preparation ASIMOMMY® increases breastmilk production in postpartum women.

ii. Output (*Endpoint*)

The output expected is that ASI MOMMY® is able to increase the production of breastmilk which in turn increases the weight of the baby after the mother receives the intervention.

b. Rationale for Sample Size and Statistical Power

Sample size is calculated using sample size formula for hypothesis testing on the average of more than two groups, unpaired numeric comparative in one measurement, are as follows (Dahlan, 2016):

$$z_{\beta} = \frac{\sqrt{v_2(2[v_1+\delta^2]^2-[v_1+2\delta^2])} - \sqrt{v_1(v_1 + \delta^2)(2v_2 - 1)F}}{\sqrt{v_1}(v_1 + \delta^2)F + v_2(v_1 + \delta^2)}$$

Information:

$n$  = number of subjects in one group

$Z_{\beta}$  = beta standard value 20 % which is 0,84

$V_1$  = degree of freedom from the number of =  $k-1$ .  $V_1 = 3-1 = 2$

$V_2$  = degree of freedom from the number of groups  $k$  ( $n-1$ ).  $V_2 = 3(n-1)$

$K$  = number of groups = 3

$$\delta^2 = \frac{n \sum (x_i - \bar{x})^2}{s^2}$$

$X_i$  = average of baby body weight in a group

$X_1$  = average of baby body weight in the domperidone and placebo group which is 3426,6 (Amri *et al.*, 2020)

$X_2$  = average of baby body weight in the placebo group which is 3221,1 (Amri *et al.*, 2020)

$X_3$  = average of three groups is 3000

$X$  = overall average (3 group)

$S$  = combined standard deviationn

$F$  = Anova table value as function of type 1,  $V_1, V_2$

Alpha = type 1 error 0,05.

i. Projected Number of Site

Locations used in this study are two sites which are Jetis and Tegalrejo Public Health Centers in Yogyakarta.

ii. Projected Number of Participant per site

Total number of subjects in one place is around 22 or 23 subjects.

c. Statistical Methods for primary and Secondary Outcomes

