### b. Safety Monitoring

Side effects will be noted by the research team starting from when the research subject signs the informed consent until three days after the last day that the subject consumed the research product. All data regarding side effect that arise is collected from the subjects and their daily cards. All side effects is noted in the Case Report Form (CRF).

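### The Day 7 visit window in the time-and-event table (0 to 14 days late) conflicts with an endpoint fixed at day 7, so the weight gain could cover 7 to 21 days of growth

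*Protocol*

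**What the plan says.** **Endpoint (Protocol, Section 2, Synopsis).** For the baseline: "Beginning of the study is on day 3 postpartum, the initial baby weight was weighed before the start of the intervention". For the follow-up: "re-weighing the baby's weight on the 7th day of the intervention". The outcome is the difference between the two weights. The Synopsis states it twice, each time as day 7 minus day 0 and without a tolerance in days.

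**Visit table (Section 3).** The Day 7 column has a visit window printed as +0 –14 days. The only row that could hold a weight is "Physical Exam (incl. temp, BP, BW", ticked under Screening/Baseline. There is no row named for the baby's weight.

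**Assessment (Section 13).** The baby is weighed before and after the intervention. No day or window is given.

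**Analysis (Section 14.d).** Numeric variables are compared by "One Way Anova test with Post Hoc Bonferroni", or by Kruskal-Wallis with Mann-Whitney if not normal. Elapsed time does not enter.

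**Supply (Section 11.b).** At the first visit mothers are "given all the drugs equivalent to the number of capsules that will be consumed for a week".

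**The concern.** One measurement has two timing rules. The endpoint text requires day 7, while the table accepts the Day 7 visit up to two weeks later. No section narrows the table's window for the weighing or says which rule prevails.

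This matters because the endpoint is a raw weight difference used as a proxy for milk production. If newborns gain weight from day to day, each day of delay adds grams that the analysis would credit to the mother's milk supply under treatment. Unequal delay adds noise to a comparison of 15 babies per arm. A difference in mean delay between arms would appear as a treatment effect. A late weighing also includes growth after the product has been used up.

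**Working it through.** **1. The protocol's own interval.** Day 0 is day 3 postpartum and the intervention lasts 7 days. 3 + 7 = day 10 postpartum, which is the day the Synopsis states. The intended interval is 7 days.

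**2. The interval that the table permits.**
- Read as 0 to 14 days late: 7 + 0 = day 7 to 7 + 14 = day 21, or day 10 to day 24 postpartum. The gain covers 7 to 21 days, up to 21/7 = 3 times the defined interval.
- Read as plus 0, minus 14: 7 − 14 = day −7 to day 7. Day −7 is 3 − 7 = day −4 postpartum, before birth, so this reading cannot be meant in full.

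The first reading is the only workable one, and under either reading the entry conflicts with the endpoint.

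**3. Added noise.** The protocol gives no daily gain. Assume a constant 20 to 40 g/day, and lateness spread evenly over the window and unrelated to growth rate.
- SD of lateness = 14/√12 = 4.04 days.
- Added SD in a baby's gain = 4.04 × 20 = 81 g to 4.04 × 40 = 162 g.
- Seven days of growth on the same assumption is 7 × 20 = 140 g to 7 × 40 = 280 g. The added SD is therefore 4.04/7 = 58% of the whole intended gain, whatever daily rate is chosen.
- Its contribution to the standard error of a difference between two arms of 15, combined in quadrature with the other variation, is √(2/15) × 81 = 30 g to √(2/15) × 162 = 59 g.

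The protocol states no SD for weight gain, so this cannot be converted into a loss of power.

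**4. Possible bias.** If mean delay differed between two arms by *d* days, the estimated difference would shift by *d* × 20 to *d* × 40 g. With *d* = 0 there is no shift.

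**5. The same calculation with a narrow window.** For lateness spread evenly over plus or minus 1 day, the SD is 2/√12 = 0.58 days, which adds 12 to 23 g.

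**The case against.** The strongest reply is that the endpoint is not in doubt. The Synopsis fixes day 7 twice, and the exclusion criteria also put completion at the seventh day of the intervention. The window belongs to a visit, and only the Synopsis places a weighing at that visit. This stands in part: day 21 is what the table permits, not what the endpoint text intends. It does not remove the contradiction, because nothing gives the Synopsis precedence and a visit on day 15 would comply with the table.

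Several stronger readings are tempting, but the document does not support them.

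- *The endpoint weighings are not scheduled.* The Synopsis and Section 13 both specify them. The weight abbreviation stands beside temperature and blood pressure and may refer to the mother. Ticks may also have been lost in the text copy: the adverse event row has none, although Section 15.b requires side effects to be recorded.
- *Other sections clash with the endpoint.* One week of product, a dropout rule for "babies who drink baby formula during the intervention" (Section 10.g.i) and side-effect recording "until three days after the last day that the subject consumed the research product" (Section 15.b) all fit a day 7 endpoint. They suggest that the table is the outlier.
- *Staff will weigh late because they schedule from the table.* No section says which document they schedule from.
- *The delay could swamp the planned effect.* A 14-day delay is 280 to 560 g on the assumed gain, and the planning means in Section 14.b, 3426.6 and the "average of baby body weight in the placebo group which is 3221,1", differ by 205.5. That sets one baby's maximum delay against a gap between group means, and those means are body weights, not gains.
- *The comparison is biased.* Subjects and research assistants are described as blinded, and no mechanism for unequal delay is stated.

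It is also fair to say that adjustment for elapsed days could sit in an SAP that is not shown. The silence of Section 14.d is therefore not itself a fault. An adjustment could not, however, turn growth after the supply ends into the endpoint as defined.

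**Conclusion.** The point holds as an internal contradiction that should be fixed. The printed Day 7 window does not agree with the endpoint under either reading, and under the workable one it lets the gain cover 7 to 21 days instead of 7. That range rests on the protocol's own figures alone.

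The added SD of about 81 to 162 g per baby is conditional on the assumed 20 to 40 g/day and on lateness spread evenly over the whole window. Bias is possible only if delay differs by arm. If all babies are weighed on day 7, as the Synopsis says, there is no effect. The missing weight ticks at Day 0 and Day 7 are a secondary matter and are not relied on.

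**What to change.** Reconcile Section 3 with the Synopsis:

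1. Replace the Day 7 window with one consistent with a day 7 endpoint, for example about plus or minus 1 day for the weighing.
2. Show the baby's weighing as its own row, ticked at Day 0 (before the first dose) and at Day 7.
3. Record the actual date of each weighing.
4. If any window is kept, analyse gain per day or adjust for elapsed days, here or in the SAP.

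The cost is a table correction and one date per weighing. No visit is added, because the Synopsis already plans the day 7 weighing at the health centres. The downside is stricter scheduling. Some weighings may still fall outside the window, and the recorded dates would allow them to be kept and adjusted.
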